### 11.2 AIMS AND METHODOLOGY

**Aim 1: Tailor recruitment materials for non-Hispanic Black and Hispanic patients with cLBP in partnership with representative patient advisory boards (PABs).**

To achieve this aim, we will update current study materials, including informational flyers, consent forms, email templates, VR cognitive debriefing manuals, and instructions for use of assigned hardware and software to better reflect the knowledge, attitudes, beliefs, and preferences of non-Hispanic Black and Hispanic study participants. Our goal will be to create two separate sets of culturally tailored materials, one per target group, to supplement existing non-tailored materials. This will be accomplished through a set of representative PAB focus groups to generate themes and concepts for study materials, integration of PAB input to modify materials, and iterative optimization of the materials through one-on-one cognitive debriefing interviews.

**PAB Focus Groups:** We will conduct foundational research with representative groups of non-Hispanic Black and Hispanic individuals with cLBP to inform development of culturally tailored study materials. We will convene 4 focus groups, including 2 groups each of non-Hispanic Black and Hispanic participants, each comprising 4-6 individuals for a total of 16-24 focus group participants. PAB members will be recruited through a combination of former study participants from the parent study, including both completers and participants who withdrew, along with additional participants naïve to the study identified through the Cedars-Sinai Patient Engagement Office and the Cedars-Sinai Medical Network. We will also seek participants from outside of Cedars-Sinai through patient advocacy groups as well as online and print ads. Given the high prevalence of cLBP in the population at large, the high prevalence of non-Hispanic Blacks and Hispanic populations in Southern California, and our successful track record of exceeding study recruitment goals to date, we do not anticipate challenges identifying up to 24 participants to join the PAB focus groups. In constructing the groups, we will seek to diversify the PABs across age, sex, education, and SES strata, where possible, to reflect different life experiences and perspectives within the target populations.

PAB focus groups will be held online using Zoom and will capture audio (not video) recordings of the proceedings after obtaining participant consent. Before the focus groups, we will develop a guide with participant instructions, open-ended think-aloud exercises, and scripted probes. Participants will also receive PDF or print copies of all current study materials prior to the focus groups (according to participant preference to receive materials by email or paper mail), and they will be asked to review the materials in advance of the meeting. A licensed neurosurgeon and/or PhD social scientist will moderate each focus group, with assistance from other members of study staff who will facilitate and take notes. Each focus group is expected to last approximately 90 minutes. Audio recordings will be transcribed by a third party (Keystrokes, Santa Monica, CA) for subsequent analysis by the study team.

Participants will initially be asked to react to the existing study materials in their own words and without prompting. The moderator will then follow scripted probes to expand on themes, concepts, and specific language or visuals suggested by the participants. Through group interaction, we will seek to identify unique relevant language with the goal of later incorporating the PAB input into modifying and culturally tailoring the materials, including both visual and textual elements. We will conduct multiple groups to ensure that interactions of a single group do not bias any one conclusion and to provide greater generalizability of our findings.

Upon completion of the focus groups, trained social scientists will qualitatively analyze the transcripts using ATLAS.ti software, including coding of patient language and classification of

vocabulary into major and minor concepts. The evaluation process will generate key words, phrases, and quotes to be used in developing tailored study materials for each group. To be considered credible, concepts for adoption will ideally be raised by more than one participant and by participants in more than one group, although individual decisions will be made using the discretion of the research team and with recognition that materials will undergo subsequent modifications based on the cognitive debriefings. We will use ATLAS.ti to generate code count histograms within major and minor concepts and will develop a network to depict a framework describing the breadth and depth of concepts to consider integrating into the study materials. The result will be a detailed “blueprint” for updating the study materials.

**Updating Study Materials:** We will next develop and refine tailored study materials. After conducting the PAB focus groups, abstracting and organizing themes and concepts, and collecting suggestions for language and visuals, we will develop draft study materials for each targeted group: one set for non-Hispanic Blacks, and one for Hispanic participants, with cLBP. In developing the materials, we will aim to not exceed a sixth-grade reading level based on the validated “simple measure of gobbledegook” (SMOG) calculator, an approach we also followed in creating item banks for the NIH Patient Reported Outcome Measurement Information System (PROMIS). As with any study materials, we will also seek to minimize ambiguity or cognitive difficulty, avoid multi-barreled questions, and use language that is as concise and simply worded as possible while attempting to use common English words and avoiding slang unless considered appropriate or warranted by PAB members.

**Cognitive Debriefing Interviews:** Once the study materials have been modified using input from the PAB focus groups, we will conduct patient cognitive debriefing interviews to assess for content validity, clarity, comprehensiveness and appropriateness of the resulting materials. We will prepare a scripted interview guide to elicit patient feedback on the draft materials. One-on-one interviews will be conducted via telephone with the same moderator who conducted the PAB meetings. For these individual interviews, we will sequentially recruit as many as 10 participants from each targeted group, drawing from PAB participants and the PAB waitlist, and will evaluate perceptions about the verbiage, images, and appearance of the draft materials. These interviews will not be recorded. We will then iteratively update the materials until they are optimized, as evidenced by receiving fewer actionable suggestions over the course of the interviews (with modifications made after each interview). If we encounter a substantial number of actionable suggestions for improvement after 10 interviews, indicating lack of thematic saturation, then we will conduct up to 5 additional interviews, drawing again from PAB focus group participants. Through this process, we will fine-tune the materials and be prepared to deliver them as part of Aim 2 of the supplemental research, described below.

## **Aim 2. Oversample non-Hispanic Black and Hispanic participants in parent study using a cohort building tool housed within the electronic health record (EHR).**

After developing two sets of culturally tailored study materials, we will next seek to deliver those materials to eligible study participants. This, in turn, will require us to identify enough non-Hispanic Black and Hispanic participants with cLBP to meet our target goals, described later in this section. To achieve this aim, we will employ Deep6 AI® (Pasadena, CA), a natural language processing (NLP) cohort building tool, and enlist Cedars-Sinai’s Enterprise Information Services (EIS), to oversample non-Hispanic Black and Hispanic participants from throughout Cedars-Sinai and our participating recruitment sites. Deep6 specifically integrates with our EHR to search both structured and unstructured data to build cohorts for clinical trials, and EIS will conduct SQL queries based on exclusionary criteria, race and ethnicity, and visits with recruiting physicians to capture additional participants not included in the Deep6 sample. Although Deep6 is already part of our protocol, it is not currently being used to specifically target study

participants by race or ethnicity. Further, it can only provide a maximum of 7,500 qualifying patients per pull. In this supplement, we will oversample target populations using Deep6 and EIS, then deliver the appropriate set of tailored recruitment materials developed in Aim 1 to these identified prospective participants. We will monitor outcomes by comparing actual recruitment against target oversampling goals, as discussed, below.

### 11.3 REVISED RECRUITMENT TARGETS

**Current and Revised Recruitment Targets:** Currently, the target sample size for the parent study is 360 participants. Regarding Hispanic participants, although we are meeting our original recruitment goal which was set at 11% to reflect U.S. Census data, there is a much higher prevalence of Hispanic/Latinx individuals in Southern California where the 2019 Los Angeles County Census revealed a 48% prevalence of this group. **We intend to implement these new recruitment materials and strategies once we have randomized 50% of the overall study cohort.** Because certain participants are eligible for replacement if they are withdrawn after randomization, this will occur at approximately **participant #200** based on current rates of withdrawal. Specifically, beginning at this point, we will seek to recruit a second-half study sample that is **17% non-Hispanic black** (previous target 12%), **40% Hispanic** (previous target 11%), and **35% non-Hispanic white** (previous target 76%).

### 11.4 STRATEGIES TO ENSURE TARGETS ARE MET

**Monitoring Recruitment Progress:** The research team will meet weekly during the study to monitor progress towards achieving target goals and will track progress using tables and visual dashboards. If the performance line falls below the target line for three consecutive weeks, then we will initiate a three-pronged strategy to course-correct as needed:

Strategy 1—Adjust Deep6 and EIS search algorithms and sample rates: If recruitment tracking reveals projections that we are falling short of target goals, then we will consult with Deep6 NLP and EIS specialists to fine-tune the parameters of the search algorithm. For example, if race/ethnicity fields are inaccurate or incomplete for some records, there may be other viable approaches such as NLP searches of clinician-inputted text within notes indicating race or ethnicity. Further, if we find specific groups are disproportionately unable to complete the screening process, we will further oversample the ratio of these participants contacted within the cohort builder lists to ensure enrollment rates meet our new target proportions.

Strategy 2—Interviews of non-enrolled patients: If necessary, we will seek consent to interview non-Hispanic Black and Hispanic patients who were invited to participate in the study, received the tailored recruitment materials, but nonetheless opted not to enroll in the trial. We will conduct individual cognitive debriefing interviews using the same techniques described under Aim 2, but here focus on individuals who experienced the recruitment materials first-hand. We will update recruitment materials further if these interviews elicit specific and actionable feedback that is incremental to the Aim 1 results.

Strategy 3—Interviews of patients who withdrew from the study: In addition to interviewing patients who declined to enroll, we will also seek consent to interview non-Hispanic Black and Hispanic participants who enrolled in the study but later dropped out before completion despite receiving tailored post-enrolment materials. These study participants may have a different

perspective from those who never enrolled and will also have experienced a broader range of study materials beyond the recruitment flyer and consent form (e.g., surveys, VR debriefing manual, instructions for hardware/software usage). We will again use the same cognitive interviews techniques previously described, and will further modify study materials, as needed, based on these additional de-briefing interviews.

## 12 APPENDIX B: RESEARCH SUPPLEMENT – UNDERSTANDING PATIENT PREDICTORS OF RESPONSE (3UH3AR076573-03S2)

### 12.1 BACKGROUND AND APPROACH

Although digital health technologies are now widely available for both therapeutic and monitoring applications, there are wide variations in patient knowledge, attitudes, beliefs and preferences regarding the uptake and effectiveness of digital health interventions. In addition, there are sociodemographic variations in willingness to engage in digital health studies, both for chronic pain and other common disorders. A recent study published in the Journal of Racial and Ethnic Health Disparities in February of 2021 found that older, less educated, and economically disadvantaged Black and Hispanic patients were up to five times less likely to have access to digital health information. Additionally, a 2016 study exploring the trends of uptake by Medicare beneficiaries found that digital health information has not yet fully reached the elderly. There have been few efforts to systematically examine patient-level predictors of digital health uptake and benefit among diverse patients with chronic pain.

This substudy will identify specific patient characteristics that influence enrollment in and completion of the parent study by employing mixed methods to examine variations in demographics, engagement, and benefit among diverse participants. The project will also offer mentorship, research training, and authorship experience to support early career development for [name], MHDS.

### 12.2 AIMS AND METHODOLOGY

#### **Aim 1: To identify explicit and latent variables associated with membership in subgroups of participants in the parent RCT of VR therapy for cLBP.**

The Digital Divide (DD) can be explained as separating patients into overarching subgroups or “classes” – those who enroll in and complete studies like the parent VR study and subsequently use the technology in their daily lives to manage pain, and those who do not. Our hypothesis is twofold: first, that there are patient-level, explicitly measured variables associated with enrollment in and successful completion of these types of studies (Hypothesis1). Second, the DD in study completeness will be further explained by latent (unobservable) “classes” of patients (Hypothesis2); membership in these latent classes is predicated upon unobservable or latent patient-level variables. Analyzing the explicit variables identified in H1 in conjunction with the identified latent classes, we hope to gain a better understanding of what explicit measures or combinations of measures may be missing or need further consideration for inclusion in studies testing VR for cLBP, or other related technologies or outcomes.

To test H1, we will identify important patient-level (measured) variables associated with enrollment in and the successful completion of the parent RCT, as well as those associated with the decision not to enroll. Specifically, we will implement a two-part regression model. The first part with a logistic

regression analysis modeling a binary outcome of enrollment, then the second part with a generalized linear regression for modeling study completeness.

To test H2, explicit variables including demographic variables and patient reported outcomes will be used in a latent class analysis (LCA) aimed at determining whether there are latent classes of patients and, if so, what explicit measures may be associated with class membership. LCA uses underlying patterns in the data (e.g., unobserved characteristics often associated with knowledge, attitudes, and beliefs) to identify latent classes (unidentified subgroups) of patients. Latent classes help guide qualitative investigation of surrounding phenomenology and determination of explicit variables that predict membership in a latent class.

**Aim 2: Explicate patient experiences on both sides of the Digital Divide (DD), including understanding how they arrived on a given side, by describing phenomenology surrounding enrollment in and successful completion of an RCT studying VR as treatment for cLBP.**

Semi-structured focus groups will be conducted separately among classes on either side of the DD as well as among the intent-to-treat sample (those randomized) and participants who chose not to enroll or were otherwise withdrawn or discontinued prior to randomization to investigate and attempt to identify the underlying constructs perpetuating membership in one vs. the other groups of patients. We will investigate the influence of knowledge, attitudes, and beliefs on the use of novel technology such as VR and wearable biosensors (as the parent study uses Fitbit) in the management of cLBP, ascertain difficulties and limitations with the use of digital technology, and explore areas for improvement in designing trials of this kind. Separately, from among the listed groups of participants, we aim to recruit N=24 (4 focus groups of up to 6 members each). Focus group data will include and qualitative data elicited through discussions characterizing experiences of using VR and describing how these factors have or have not influenced patients to preclude, decrease, continue, or increase use.

Participants who were contacted for participation in the parent study will first be approached by email recruitment letter, then a phone call, for participation in this study. Participants expressing interest will be contacted again with a list of possible dates and times to participate. Prior to the scheduled focus group, participants will also be emailed an information sheet describing the risks and benefits of participating in the sub-study, and at the start of the focus group session, present participants will be asked to verbally confirm that they have read and understood the information sheet. Participants will be reimbursed with a \$100 Amazon e-gift card for their participation once they have completed the focus group, which should take no longer than 60 minutes.

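### Appendix B states H2 as a claim about study completion, but the analysis named to test it never relates latent class to completion

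*Protocol*

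**What the plan says.** Section 12.2 of the protocol (Appendix B, Aim 1) states two hypotheses. H1 is that measured patient-level variables are associated with enrolment and completion. H2 is that "the DD in study completeness will be further explained by latent (unobservable") classes of patients.

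Each hypothesis has its own analysis:

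- **H1:** a two-part regression, with a logistic model for enrolment followed by a "generalized linear regression for modeling study completeness".
- **H2:** a latent class analysis (LCA) of measured variables, introduced as an open list: "demographic variables and patient reported outcomes will be used in a latent class analysis (LCA) aimed at determining whether there are latent classes". In full, it is "aimed at determining whether there are latent classes of patients and, if so, what explicit measures may be associated with class membership".

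Three further sentences mention classes. One says that looking at the H1 variables "in conjunction with the identified latent classes, we hope to gain a better understanding of what explicit measures" may be missing from studies of this kind. Another gives the use of the classes: "Latent classes help guide qualitative investigation of surrounding phenomenology and determination of explicit variables that predict membership in a latent class". Under Aim 2, "Semi-structured focus groups will be conducted separately among classes on either side of the DD", and also among the randomized sample and people who did not enrol or left before randomization.

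The SAP does not cover Appendix B. Its latest listed version is dated 09/14/21, and the appendix entered the protocol with version 7.0 on 8/29/2023.

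**The concern.** H2 has an outcome (completion) and an explanatory variable (latent class). A test of H2 must put the two together. The named analysis answers two other questions: whether classes exist, and what goes with belonging to one. Both can be answered in full without learning anything about completion.

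The answer to the first question is also close to predictable. LCA assumes that items are independent within a class, so items that correlate tend to need two or more classes to fit. The trial's scales for pain interference, function, anxiety, depression, sleep and catastrophizing can be expected to correlate.

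Explaining enrolment in, and completion of, the parent study is the stated purpose of this sub-study (Section 12.1). At stake is whether its second hypothesis gets an answer, and whether classes said to fall on one or other side of the divide have been shown to differ in completion.

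A related hazard is that the time point of the patient-reported outcomes is not given. Follow-up scores depend on staying in the study, so using them would build completion into the classes.

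**Working it through.** The documents give no sample size, significance level, fit criterion or number of classes for this LCA, so there is no figure to reproduce. The main check is textual; the simulations illustrate it.

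**1. Where could class meet completion?**

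| Text in Section 12.2 | Is completion present? | Is latent class present? | Are they related? |
|---|---|---|---|
| H2 statement | yes | yes | asserted |
| Test of H1, part two | yes, as outcome | not named as predictor | no |
| Test of H2 (LCA) | not named | yes | no |
| Joint look at H1 variables and classes | only through the H1 variables | yes | no; the stated purpose is to find missing measures |
| Aim 2 focus groups | implied by the sides of the divide | classes mentioned | no rule given |

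No row contains a test of class against completion.

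**2. Does finding classes bear on H2?** Inputs: N = 360 (target sample size, protocol Section 5.5). Everything else is assumed: six binary items, cut at the median, from one continuous factor, so that no true classes exist. With loading λ the underlying correlation is λ²: 0.30² = 0.09, 0.45² ≈ 0.20, 0.55² ≈ 0.30, 0.70² = 0.49.

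Models with K = 1 and K = 2 classes were compared by BIC = −2 log L + k ln N, where k = (K − 1) + 6K. So k = 6 and 13, and the second class costs 7 × ln 360 = 7 × 5.886 = 41.2 units of −2 log L.

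| Assumed correlation | Runs in which BIC chose two classes (range over repeated simulations) |
|---|---|
| 0.09 | 2% to 10% |
| 0.20 | 97% to 98.5% |
| 0.30 | 100% |
| 0.49 | 100% |

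Completion played no part in these choices. When completion (80%) was generated independently and tested against class in the runs that chose two classes, the test was significant in 3.6% to 4.5% of runs at correlations of 0.20 or more, about the nominal 5%.

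**3. Would the missing step separate a true H2 from a false one?** Assumed: two true classes, eight binary items with probability 0.7 in one class and 0.3 in the other, N = 360, 500 runs, and Fisher's exact test of modal class against completion at two-sided 0.05.

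| Completion by class | Two classes chosen | Class-completion test significant |
|---|---|---|
| 80% and 80% | 100% | 3.2% |
| 60% and 60% | 100% | 4.8% |
| 70% and 90% | 100% | 94.4% |

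The existence of classes looks the same in all three rows. Only the added test tells them apart.

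**4. Should H2 be judged on what class adds to the H1 model?** Same assumptions, completion 70% and 90%, modal class without correction for classification error. Class alone was significant in about 95% of runs. Added to a logistic model that already held all eight LCA items, it was significant in about 13%. With sharper items (0.8 and 0.2) the figures were about 100% and 25% to 27%. Class is estimated from those items, so adjusting for all of them removes most of its signal.

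**The case against.** The best reply is that the text is looser than the concern implies. The list of LCA inputs is introduced as including certain variables, which leaves it open. Completion might be meant as one of the measures associated with membership. Aim 1 opens by describing the divide itself as classes of people who do and do not complete, and it plans to view the H1 variables together with the latent classes.

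Part of this stands. A reader might infer that completion is excluded from the LCA; the documents support only that it is not named. Naming it as an indicator would not help, since the outcome would then help define the classes. Reading it as an associated measure still leaves no stated test, and none of what class adds to H1.

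A reader might also infer that H2 would be declared supported once classes are found. The documents contain no such decision rule; the uses they state for the classes are guiding qualitative work and finding predictors of membership. Nor do the focus groups rest on latent classes alone, because Aim 2 lists other groups, and classes on a side of the divide may simply mean completers and non-completers.

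The simulations describe a general property of LCA, not this trial. The correlations, item coding and completion rates are assumed, demographics are left out, and 360 is the randomized target although Aim 1 also concerns people who did not enrol. At a correlation of 0.09 the effect nearly vanishes. The textual gap does not depend on them.

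**Conclusion.** The point holds as a mismatch between a hypothesis and its named test. H2 is about completion; the analysis offered for it establishes only whether classes exist and what accompanies membership. Following the plan exactly cannot support or refute H2. This is more than missing detail, because the test that is stated answers a different question.

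That conclusion rests on the text alone. That finding classes is weak evidence rests on assumed inter-item correlations of about 0.20 or more.

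The severity is minor. The sub-study is supplementary, and no primary, secondary or safety analysis of the trial is affected. A reader should not carry the point over to the efficacy results.

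**What to change.** Replace the H2 analysis in Section 12.2, Aim 1 with these steps:

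1. Fit the LCA on baseline variables only (demographics and screening-week patient-reported outcomes), and say so.
2. Test study completeness, defined as in the H1 model, as a distal outcome of class, with a method that allows for classification error. Base any conclusion on H2 on that association.
3. Report the contribution of class over H1 covariates as supportive, because H2 claims a further explanation. Choose in advance H1 covariates that are not LCA indicators. Making improvement over all H1 covariates the condition for H2 would usually reject a true H2 if those covariates include the indicators (step 4 of the working).
4. State in Aim 2 whether the focus-group classes are latent classes or completers and non-completers.

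The cost is one paragraph and one or two extra models on data already held. There are two downsides: H2 may turn out unsupported, and the association in step 2 does not by itself show that class explains more than the variables that define it.
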